1 BACKGROUND [REDACTED]

[REDACTED]

[REDACTED]

[REDACTED]

[REDACTED]

IIM who had persisting signs of active disease after treatment with glucocorticoids and one

[REDACTED]

Research Hypothesis:

Subcutaneous abatacept (125mg weekly) in combination with standard treatment will achieve a higher rate of responders, defined as the percentage of subjects who achieve the IMACS DOI (International Myositis Assessment and Clinical Studies - definition of improvement), after 24 weeks of treatment versus standard treatment alone in adult subjects with active IIM.

Schedule of Analyses:

The analyses for this study is scheduled to be performed at 4 separate time points:

- 1) End of Double-Blind period (Week 24) for all subjects.
- 2) End of Open-Label period (Week 52) for all subjects.
- 3) End of Open-Label Extension period (Week 76) for sites in Japan. The purpose is to obtain 52 week abatacept efficacy data on all Japanese subjects for submission, specifically here the Japanese subjects originally randomized to placebo.
- 4) End of the study (completion of Long-Term Extension period and Follow-up period).

The Double-Blind period (Week 24) analysis will be performed once all subjects complete their Week 24 visit assessment or discontinue prematurely prior to Week 24. The Week 24 analysis will include the analyses of the primary efficacy endpoint, secondary and exploratory efficacy endpoints up to Week 24 and safety analyses. A subgroup analysis (selected outputs identified in DPP) on Japan subjects alone will be conducted for Japanese submission purposes. Actigraphy data and data from the Muscle Biopsy sub-study will be not be part of the initial Double-Blind period (Week 24) database lock and will be reported separately.

The Open-Label period (Week 52) analysis will be performed once all subjects complete 52 weeks of treatment in the study. A subgroup analysis (selected outputs identified in DPP) on Japan subjects alone will be conducted for Japanese submission purposes.

The Open-Label Extension period (Week 76) analysis will be performed, using only Japanese sites, once all Japanese subjects complete their Week 76 visit assessment. Selected outputs only identified in DPP.

The final analysis will be performed when all subjects have completed the 3 year long-term extension, (3.5 years for Japan subjects by including OLE data) and/or follow-up visits whichever is later.

This Statistical Analysis Plan provides details of the Week 24 analysis; details of the 3 other analyses are provided in [APPENDIX 3](#).

In addition to these analyses, interim analyses are performed for the external, independent Data Monitoring Committee (DMC). The DMC was formed and charged with assessing the safety of Abatacept on a regular basis. The contents and methods of reports to the DMC are outlined in the DMC Charter⁶.

2 STUDY DESCRIPTION

2.1 Study Design

This is a 24-week, Phase 3, randomized, double-blind, placebo-controlled, multicenter, study in subjects with active Idiopathic Inflammatory Myopathy (IIM; e.g., DM, PM, autoimmune necrotizing myopathy) on standard background treatment.

In addition to the 24-week double-blind period, the study includes:

- A 28-week open-label (OL) treatment period during which all subjects will receive SC abatacept with background treatment.
- An additional 24-week open-label of SC abatacept with continued therapy from the original OL period for subjects in Japan.
- A 3-year long-term extension of SC abatacept (156 weeks) with background treatment for all subjects except subjects in the U.S. and the Czech Republic.

The primary objective for this study is to compare the clinical efficacy of weekly abatacept in combination with standard treatment to standard treatment alone by assessing the percentage of subjects who achieve the IMACS DOI after 24 weeks of treatment versus standard treatment alone in adult subjects with active IIM.

Written informed consent must be provided by the subjects prior to undergoing any procedures during the screening phase.

Subjects who meet the study inclusion criteria enter into the 24-week Double-Blind (DB) period. During the DB period, approximately 150 subjects will be randomized in a 1:1 ratio to one of two treatment groups in a double-blinded manner as follows:

- Group A: Active Abatacept SC (125mg) weekly + standard treatment.
- Group B: Placebo Abatacept SC weekly + standard treatment.

At the time of randomization, subjects must be on a stable background treatment for IIM (“standard treatment” as defined in Section 3.4.1.1 of the protocol). No adjustment in background treatment will be allowed during the DB period.

During the 24-week DB period, subjects in either treatment group who meet the criteria for worsening (as defined in protocol Section 3.1.4) at any visit between Weeks 12 and 24 are permitted to use rescue therapy. The choice of rescue therapy is at the discretion of the investigator; however, rescue treatment may not be abatacept or a prohibited medication. Rescued subjects will remain blinded to study medication through Week 24 and will begin Open-Label (OL) abatacept treatment period after Week 24, however they will be considered not to have achieved the IMACS DOI for the purpose of the primary efficacy analysis.

The 24-week DB period is followed by a 28-week OL abatacept treatment period (OL period). During this period, subjects initially randomized to receive the combination of abatacept and standard treatment will continue this regimen. Subjects who are initially assigned to receive standard treatment alone will be switched to standard treatment plus abatacept. For the purposes of obtaining 1 year efficacy data in all Japan subjects (specifically for placebo randomized subjects) there will also be a 24-week open-label extension for subjects randomized in Japan. Background treatment may be adjusted (including the dose of corticosteroids and immunosuppressant’s) at any time during the OL period. Use of immune globulin (intravenous [IVIG] or subcutaneous [SCIG]) is permitted during this period. Addition of any other prohibited medication is not permitted.

There will be a 3 year long-term extension period for subjects randomized in countries other than the U.S. and the Czech Republic. All subjects will receive standard treatment plus abatacept.

At the conclusion of the study, subjects who continue to demonstrate clinical benefit with study drug, i.e. abatacept, will be eligible to receive BMS supplied study drug based on local regulations.

In addition, subjects who discontinue treatment with study medication during the double-blind period will complete the Early Termination visit (which is the same visit as Day 169 visit). These subjects must also return for the double-blind period Day 169 post-randomization to complete the post-study drug efficacy visit. Subjects must also complete 2 follow-up visits (85 and 169 days after the last dose) during the 24-week post-treatment follow-up period, to perform safety and laboratory assessments. This period begins on the day of the Early Termination visit and applies only to subjects who do not start commercial abatacept therapy.

Subjects who discontinue treatment with abatacept during the open-label period or open-label extension for Japan will complete the Early Termination visit for the OL and 2 follow-up visits during the 24 week post-treatment follow-up period, to perform safety and laboratory assessments. If the subject receives treatment with an alternative source of abatacept, completing this post-treatment follow-up period is not required.

Subjects who discontinue treatment with abatacept during the long-term extension period will complete the Early Termination visit for the OL and two follow-up visits to perform safety and laboratory assessments. If the subject receives treatment with an alternative source of abatacept, completing this post-treatment follow-up period is not required.

2.2 Treatment Assignment

At the time of enrollment, immediately after written informed consent is obtained and before performing any study-related procedures, each subject will be assigned a unique sequential subject number beginning with 001, 002, 003, etc. for identification throughout the study by Interactive Recognition System (IxRS). This subject number must not be reused for any other participant in the study. The physician/coordinator must contact the Central Randomization System to enroll each subject into a centralized database at the beginning of the study (Screening Visit).

Randomization schedules were generated and kept by the Randomization Group within Drug Supply Management of Bristol-Myers Squibb. Each subject who is qualified for treatment is assigned a unique randomization number by IxRS. A randomization number will be assigned in the order in which subjects qualify for treatment, not in the order of study enrollment (screening visit).

Randomization will be stratified globally by 3 stratification variables: (1) Dermatomyositis (DM) vs. non-DM IIM, and (2) presence or absence of interstitial lung disease (ILD), (3) Japan vs. Rest of World (ROW).

Subjects are randomized in a 1:1 ratio within each of the strata to the abatacept or placebo treatment groups across all sites. Specific instructions for randomization into the Central Randomization System were provided in a separate manual.

Throughout the 24-week DB period of the study subject treatment assignment will remain blinded to clinical Investigational staff not involved in the preparation of the study medication.

2.3 Blinding and Unblinding

The subjects and clinical assessor(s) are not aware of which treatment is being administered to the subjects enrolled in the study. The pharmacist (or qualified drug preparation person) will be unblinded to study medication (SC Abatacept or SC placebo). The pharmacist (or qualified drug preparation person) know the scheduled assignments and would dispense the appropriate treatment accordingly.

Blinding is critical to the integrity of this clinical drug trial. However, in the event of a medical emergency or pregnancy in an individual subject, in which knowledge of the investigational product is critical to the subject's management, the blind for that subject may be broken by the treating physician.

Before breaking the blind of an individual subject's blinded treatment, the Investigator should determine that the information is necessary, i.e., that it will alter the subject's immediate management. In many cases, particularly when the emergency is clearly not investigational product-related, the problem may be properly managed by assuming that the subject is receiving active product without the need for unblinding.

BMS personnel will be blinded to treatment assignment until all subjects have completed the double-blind period, the database is locked for analysis (Week 24 analysis) and assessments of the primary efficacy endpoint are made.

2.4 Protocol Amendments

The table below summarizes the main purpose of each of the protocol amendments relevant to the analyses in this SAP. See the amendment for further details.

Table 2.4-1: Protocol Amendments

Document	Amendment Date	Main Purpose of Amendment
Amendment 02	10-Mar-2017	Clarify target disease population, exclusion criteria and rules for performing HRCT in at risk subjects.
Revised Protocol 03	09-May-2018	Clarify language, adjust criteria to improve subject selectio [REDACTED]

Table 2.4-1: Protocol Amendments

Document	Amendment Date	Main Purpose of Amendment
Revised Protocol 04	01-Feb-2019	Addition of descriptions for the Open Label Extension Period for Japan and the Long Term Extension Period.

3 OBJECTIVES

3.1 Primary

The primary objective for this study is to compare the clinical efficacy of weekly abatacept in combination with standard treatment to standard treatment alone by assessing the percentage of subjects who achieve the IMACS DOI by Week 24 compared to baseline, defined as:

- An improvement of $\geq 20\%$ in 3 IMACS core measures, AND
- No more than 2 IMACS core measure scores worsen by $\geq 25\%$, AND
- Manual Muscle Test (MMT-8) may not decrease by $\geq 25\%$.

3.2 Secondary

- 1) To assess the clinical efficacy of weekly abatacept in combination with standard treatment to standard treatment alone by assessing the change in muscle endurance test using the Myositis Function Index (FI-2) from baseline to Week 24.
- 2) To assess the efficacy of abatacept in combination with standard treatment to standard treatment alone by assessing the mean change in functional disability using the Health Assessment Questionnaire-Disability Index (HAQ-DI) from baseline to Week 24.
- 3) To assess the efficacy of abatacept in combination with standard treatment to standard treatment alone by assessing the mean change in extra-muscular disease activity as defined by Myositis Disease Activity Assessment Tool (MDAAT) from baseline to Week 24.
- 4) To assess the efficacy of abatacept in combination with standard treatment to standard treatment alone in achieving improvement on the Myositis Response Criteria from baseline to Week 24.

[REDACTED]

[REDACTED]

[REDACTED]

4 ENDPOINTS

4.1 Primary Efficacy Endpoint

The primary endpoint for this study is the proportion of subjects who achieve IMACS DOI (as defined in [Section 8.1.1](#)) at Day 169 (Week 24) without rescue therapy.

4.2 Secondary Efficacy Endpoints

- 1) Mean change in muscle endurance using the myositis function index scores (FI-2) from baseline to Day 169 (Week 24).
- 2) Mean change in Health Assessment Questionnaire-Disability Index (HAQ-DI) from baseline to Day 169 (Week 24).
- 3) Mean change in Myositis Disease Activity Assessment Tool (MDAAT), based on the extramuscular disease activity VAS, from baseline to Day 169 (Week 24).
- 4) Myositis Response Criteria (MRC) total improvement score at Day 169 (Week 24).

4.3 Safety Endpoints

- 1) All adverse events (AEs/SAEs).
 - 2) AEs of interest (serious infections, malignancies, injection site reactions, systemic reactions).
 - 3) Laboratory test abnormalities.
- [REDACTED]
- [REDACTED]
- [REDACTED]

[REDACTED]

5 SAMPLE SIZE AND POWER

A sample size of 150 subjects (75 subjects per treatment group) is planned based on the primary comparison of the proportion of subjects with IMACS DOI (as defined under the primary objective) at Day 169 (Week 24) between the SC abatacept and the SC placebo groups on a background of standard treatment.

A sample size of 150 subjects randomized in a 1:1 ratio to the SC abatacept group and SC placebo group will yield a power of approximately 90% to detect a treatment difference of 27% in the rate of IMACS DOI between the 2 treatment groups based on a continuity corrected chi-squared test. This power estimate assumes a two-sided alpha level of 5%, IMACS DOI rate of 60% in the abatacept group and 33% in the placebo group. The 60% estimate of IMACS DOI in the abatacept

group was based on reported rates of IMACS DOI in studies of patients with Myositis on combination therapy with another biologic agent. It is expected that the rate of IMACS DOI on abatacept in combination with standard treatment should be similar to that observed with the use of another biologic agent in combination with standard treatment. Table 5-1 below presents the power estimates for other considerations of proportion of subjects in IMAC DOI in the abatacept group assuming the total sample size of 150 subjects. Randomization will be stratified globally by 3 stratification variables: (1) disease diagnosis (Dermatomyositis [DM] vs. non-DM IIM), (2) Interstitial Lung Disease (ILD) (present vs. absent), (3) Japan vs. ROW.

Table 5-1: Estimates of Power for Various Assumed Rates of IMACS DOI at Week 24 Assuming Total sample Size of 150

Abatacept Rate	Placebo Rate	Delta	Power (%)
50%	20%	30%	96
	25%	25%	85
55%	25%	30%	95
	30%	25%	84
60%	25%	35%	~ 99
	30%	30%	95
	35%	25%	83

6 STUDY PERIODS, TREATMENT REGIMENS AND POPULATIONS FOR ANALYSES

6.1 Study Periods

There are 6 analysis periods defined for the study: the 5 study periods ((i) pre-treatment period; (ii) 24-week DB period; (iii) the OL period; (iv) the OLE period for Japan; (v) the LTE period, incorporating the OLE period for Japan) and (vi) the cumulative abatacept period. These periods will be used in the safety summaries.

The pre-treatment period: covers the time period prior to the first dose date/time of study medication.

The 24-week Double-Blind period: starts at the first dose date/time of double-blind study medication and lasts until the last dose date of the double-blind period + 56 days if subjects discontinue the study during double-blind period, or until the first dose in the open-label period.

Since the dosing information for the Open-Label period, the Open-Label Extension period and the Long-Term Extension period is recorded on the same CRF page, it is not possible to derive the first/last dose for the different periods based on that CRF page. This is why start and end visit dates from other CRF pages will be used to distinguish between these 3 periods. Start and end visit dates are recorded for most periods, except the start of the OLE period for Japan subjects, this will be

assumed to be the end of the OL period. These dates will be used for deciding which dose belongs to which period.

The Open-Label period: starts at the first dose of the open-label period and lasts until the last dose date of open-label period + 56 if subjects discontinue the study during open-label period (or if subjects are from U.S. and Czech Republic sites), or until the first dose in the open-label extension period for subjects from Japanese sites, or the first dose in the long-term extension period for subjects from other sites.

The Open-Label Extension period (Japan subjects only): starts at the first dose of the open-label extension period (determined as the open-label period end visit date from the CRF) and lasts until the last dose date of open-label extension period + 56 if subjects discontinue the study during open-label extension period, or until the first dose in the long-term extension period.

The Long-Term Extension period (all subjects except for U.S. or Czech subjects): starts at the first dose of the long-term extension period and last until the last dose date of long-term extension period + 56.

The cumulative abatacept period: starts at the first dose date/time of abatacept and lasts until the last dose date of abatacept in the study + 56 days. For subjects randomized to placebo in the double-blind period the first dose date of abatacept will be the first dose date in the open-label period.

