11.5.1.1 Open-Label Period Exposure

The extent of exposure for the open-label period will be calculated and presented in days as follows:

- For subjects who discontinued during the open-label period or did not enter the open-label extension period or the long-term extension period within 56 days of the last injection in the open-label period:
- Exposure in days = (date of last injection in the open-label period - date of first open-label injection + 1) + 56.

For subjects who enter open-label extension or long-term extension period within 56 days of the last injection in the open-label period:

- Exposure in days = (date of first injection in the open-label extension or long-term extension period - date of first open-label injection).

The offset of 56 days is the length of 2 regular dosing cycles and represents approximately 4 times the half-life of Abatacept in humans.

Summaries of exposure to study drug will show the distribution of the number of injections and days on drug, together with the means, standard deviations, medians, minima and maxima, by treatment group.

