11.5.1.4 Cumulative Abatacept Exposure

The cumulative abatacept exposure will only be computed for the final analysis (i.e. at the study closeout); the exposure to abatacept during the cumulative period will be calculated as follows:

Exposure in months = (date of last dose of abatacept in the study - date of first dose of abatacept in the study + 1 - adjustment + 56)/30.

The offset of 56 days represents approximately 4 times the half-life of abatacept in humans.

Adjustment is the sum of the time span between:

- the last dose of abatacept in the double-blind period and the first dose of abatacept in the open-label period which exceeds 56 days (all sites),
- the last dose of abatacept in the open-label period and the first dose of abatacept in the open-label extension period which exceeds 56 days (Japan sites); or the last dose of abatacept in the open-label period and the first dose of abatacept in the long-term extension period which exceeds 56 days (all other sites but not including U.S. and Czech Republic sites),
- the last dose of abatacept in the open-label extension period and the first dose of abatacept in the long-term extension period which exceeds 56 days (Japan sites).

Summaries of cumulative period exposure to study drug will show the distribution of the number of months on drug, together with the means, standard deviations, medians, minima and maxima, by treatment group. A listing of abatacept study medication dose dates will also be provided for the cumulative period.

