Exposure adjusted (per 100 person-years) incidence rates of adverse events accounting for multiple occurrence of an event will be calculated for all AEs/SAEs which occurred during the open-label / open-label extension / long-term extension periods in abatacept treated subjects. The numerator is the number of unique events within the open-label / open-label extension / long-term extension periods (up to 56 days post last abatacept dose during the open-label / open-label extension / long-term extension periods). The denominator is the overall total exposure (person-years) within each period, which is calculated as the sum over all subjects of exposure (in days) divided by 365.25. The resulting incidence rate is multiplied by 100 to express the rate per 100 person-years.

As an example, if 10 patients report 7 unique episodes of headache and had a combined cumulative exposure of 20 years to study medication, the incidence rate is reported as $7 / 20 * (100)$ or 35 cases per 100 patient years of exposure.

For all SAEs, exposure adjusted per 100 person-years rates will be summarized by time-intervals in months: 0-3 months, 3-6 months, 7-9 months, 10-12 months and > 12 months (time-intervals defined as Days 1-90, Days 91-180, Days 181-270, 271-360 and > 360 Days), respectively. In addition, the number of subjects who experienced a SAE, once or multiple times within this period will be presented. The above analyses will be performed for infection and local injection site reaction, respectively. A subject listing of unique AEs will also be provided.

Unique AEs and exposure adjusted multiple events summaries will also be provided separately for the cumulative period. The exposure adjusted per 100 person-years rates will be provided for SAEs, Infections, local injection site reaction. and will be summarized by 3 month time interval for the cumulative period: 0-3 months, 3-6 months, 7-9 months, 10-12 months and > 12 months (time-intervals defined as Days 1-90, Days 91-180, Days 181-270, 271-360 and > 360 Days), respectively.

[REDACTED]

[REDACTED]

- █ [REDACTED]
- █ [REDACTED]
- █ [REDACTED]
- █ [REDACTED]
- █ [REDACTED]

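### Cumulative abatacept AE rates can count events in between-period gaps whose person-time the exposure formula removes

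*SAP*

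**What the plan says.** **Event window.** SAP 6.1 lists six analysis periods and states: "These periods will be used in the safety summaries". For cumulative abatacept, the window "starts at the first dose date/time of abatacept and lasts until the last dose date of abatacept in the study + 56 days". Protocol 8.4.7 and 8.4.9 give the same start and end for the cumulative safety summaries. None of these sections sets aside off-drug time in between.

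**Exposure.** SAP 11.5.1.4 takes the date of the last abatacept dose minus the "date of first dose of abatacept in the study + 1 - adjustment + 56", divided by 30 to give months. The adjustment sums time spans at each transition. The first span is bounded by two doses: "the last dose of abatacept in the double-blind period and the first dose of abatacept in the open-label period which exceeds 56 days". The others cover open-label to Japan extension or long-term extension, and Japan extension to long-term extension.

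**Rates.** SAP 11.7 defines exposure-adjusted rates for the open-label, Japan extension and long-term extension periods, with the numerator limited to 56 days after the last dose in the period. It then adds: "Unique AEs and exposure adjusted multiple events summaries will also be provided separately for the cumulative period". That paragraph asks for rates by 3-month interval and has no numerator limit.

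**Single periods.** In SAP 6.1 the double-blind period of a continuing subject lasts "or until the first dose in the open-label period", whatever the gap. The open-label period ends at the first Japan extension dose, "or the first dose in the long-term extension period for subjects from other sites". The open-label exposure formula in SAP 11.5.1.1 instead stops 56 days after the last injection for anyone who "did not enter the open-label extension period or the long-term extension period within 56 days of the last injection in the open-label period".

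**The concern.** A rate per 100 person-years needs its events and its person-time to come from the same days. For a subject who restarts abatacept more than 56 days after the last dose of the preceding period, the cumulative event window includes the whole gap and the cumulative exposure does not. An infection or a flare in the removed part of the gap enters the numerator with nothing in the denominator to match it.

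The cumulative tables are the long-term safety result of the trial. The SAP applies a matching 56-day limit to the other three sets of rates, so its absence here looks like an omission. A programmer who follows 6.1, 11.5.1.4 and 11.7 literally would produce mismatched rates.

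**Working it through.** **Step 1. The plan's own rate.** The example in SAP 11.7 has 7 unique events over 20 person-years: 100 × 7/20 = 35 per 100 person-years. This reproduces.

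Suppose 1 of the 7 events fell in removed gap time. With the gap out of both parts, the rate is 100 × 6/20 = 30. If instead the gap were 1 person-year and kept in both parts, it is 100 × 7/21 = 33.3. The plan as written would report 35.

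**Step 2. Direction.** Let E be events in exposed time, e events in removed gap time, T exposure and G removed time. The planned rate is (E + e)/T. It is never below E/T (gap out of both) or (E + e)/(T + G) (gap in both). The error can go only upward.

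**Step 3. One affected subject.** Take a subject outside Japan on abatacept from Day 1.

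- Last open-label dose in Week 51 (Protocol 4.5.1): 51 × 7 + 1 = Day 358.
- Gap g: days from that dose to the first extension dose.
- Last extension dose on extension Day 1086 (Protocol 4.5.1): 1085 days after the first.
- Event window: 358 + g + 1085 + 56 = 1499 + g days.
- Exposure when g exceeds 56: 1499 + g − (g − 56) = 1555 days if only the excess over 56 days is removed, or 1499 days if the whole span is removed. The wording of 11.5.1.4 allows either reading.
- With a regular weekly gap, g = 7, window and exposure are both 1506 days and there is no bias.

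Assuming the same event rate inside and outside the gap, the overstatement is window/exposure − 1:

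| g (days) | Window | Excess removed (1555) | Whole span removed (1499) |
|---|---|---|---|
| 90 | 1589 | +2.2% | +6.0% |
| 180 | 1679 | +8.0% | +12.0% |
| 365 | 1864 | +19.9% | +24.4% |

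**Step 4. The cohort.** Let a share f of subjects have the gap and the rest have 1506 days. The overstatement is f × (window − exposure) / [f × exposure + (1 − f) × 1506].

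- Low end, f = 5%, g = 90, excess removed: 0.05 × 34 / (0.05 × 1555 + 0.95 × 1506) = 1.7/1508.45 = 0.1%.
- Middle, f = 10%, g = 180, excess removed: 0.10 × 124 / (0.10 × 1555 + 0.90 × 1506) = 12.4/1510.9 = 0.8%.
- High end, f = 10%, g = 365, whole span removed: 0.10 × 365 / (0.10 × 1499 + 0.90 × 1506) = 36.5/1505.3 = 2.4%.

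Both f and g are assumptions; neither document gives them.

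**Step 5. Intervals.** SAP 11.5.1.4 makes one subtraction from total exposure. Nothing says which 3-month interval loses the days, so no interval-level figure can be derived.

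**The case against.** The strongest reply is that the gaps may hardly exist. Open-label Day 169 is the double-blind Day 169 visit (Table 5.1-3), Japan extension Day 365 is the open-label Day 365 visit (Table 5.1-5), and long-term extension Day 1 is the day of the last open-label visit (Table 5.1-6). A 56-day gap spans about eight weekly doses, and Protocol 3.5 already requires discontinuation after five consecutive missed doses in Weeks 24-52. The summaries are also descriptive. This stands as a limit on size. It does not remove the mismatch, because the SAP itself provides for such gaps at every transition.

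A second reply is that 11.7 never names the 11.5.1.4 formula as the cumulative denominator: one section works in days/30, the other in days/365.25. That is correct, and the link is an inference. No other cumulative exposure is defined.

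A reader might infer that the single-period results are inflated too, since 6.1 runs those periods to the next first dose and gives no end date for an open-label completer outside Japan, the U.S. and the Czech Republic who declines the extension. The documents do not support that. SAP 7 and 7.6.1 limit double-blind events to 56 days after the last dose, Protocol 8.4.7 and 8.4.9 do so for the open-label and long-term summaries, and SAP 11.7 does so for the open-label, Japan extension and long-term rates. What remains is a conflict of wording with 6.1.

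A reader might also infer that gap events should leave every cumulative table. An n (%) table uses no person-time, so it has no mismatch, and Protocol 8.4.7 and 8.4.9 require all AEs from first dose to 56 days after the last.

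**Conclusion.** The inconsistency is real for the cumulative exposure-adjusted rates, overall and by 3-month interval, and no section resolves it. Its direction is fixed: against abatacept, never in its favor. Its size depends on gaps that the documents do not count. It is zero with on-schedule transitions, about 2-24% for a subject with a 90-365 day gap, and about 0.1-2.4% for the cohort if 5-10% of subjects have such gaps. These figures assume equal event rates inside and outside the gap and a subject outside Japan treated to the end of the extension. They also take the 11.5.1.4 exposure as the denominator.

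It would go too far to say that the cumulative rates are overstated as a matter of fact, which requires gaps that contain events. A large error in a particular 3-month interval is possible but cannot be quantified. Dosing interruptions within a period are not part of this point, because SAP 11.5.1 ignores them in exposure and they stay in both numerator and denominator.

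**What to change.** 1. In SAP 11.7, for the cumulative exposure-adjusted rates, overall and by 3-month interval, count only AEs with onset in time that contributes to the 11.5.1.4 exposure. Events more than 56 days after the last dose before a between-period gap, and before the next dose, leave the rate numerator and are listed separately.
2. In SAP 11.5.1.4, state that the adjustment is the excess over 56 days, and remove those days from the interval in which they fall. In 11.7, name this exposure, in days/365.25, as the cumulative denominator.
3. Leave the cumulative n (%) tables as Protocol 8.4.7 and 8.4.9 define them.
4. In SAP 6.1, align the double-blind, open-label and Japan extension period ends with the 56-day limits stated elsewhere, including for open-label completers who do not enter the extension. This is an alignment of wording only.

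The cost is SAP text, one condition in the event flag for the cumulative rates, allocation of the removed days to intervals, and one listing. No protocol change is needed, and no safety event drops out of the report.
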